C5.4. Secondary Outcomes

Post-intervention Treatment Engagement. With HIPAA authorization, information from participants' VA administrative data will be extracted to assess if treatment condition relates to engagement in specialty mental health and substance use visits. Number of visits attended and prescriptions of psychiatric and substance use medications between enrollment and 20 week follow-up will be extracted for each participant. Drs. [name] and [name] have expertise in this type of data extraction. In addition, participants will be asked about non-VA treatment at each assessment point using the Treatment Services Review⁸⁶.

C6 Treatment Conditions

C6.1. Experimental Condition: PC-TIME. Participants randomized to the PC-TIME condition will participate in the intervention developed in the earlier study phases (see C1.2). Sessions will be conducted in-person and will be recorded for the purpose of monitoring protocol adherence.

C6.2. Control Condition: PC-TAU. PC-TAU consists of mandatory annual screens for all patients with the

AUDIT-C and PC-PTSD. Patients who score a 4 or higher on the AUDIT-C receive a Brief Advice intervention from their PC medical provider that is built into the electronic medical record as a mandatory response to a positive screen. In addition, patients who score positive on the AUDIT-C or PC-PTSD are offered a referral to the PCMHI provider within the PC clinic. PCMHI in VA consists of licensed, independent providers (typically psychologists or clinical social workers) providing brief assessment and interventions to veterans and consultation to other members of the PC team. Patients are often treated in PC for a few sessions then referred to specialty mental health and substance abuse care, if problems persist. On average, 4 PCMHI sessions are provided to PTSD patients typically focused on assessment, psycho-education, and supportive counseling ¹⁰. VA PC patients often decline referrals for alcohol use following the receipt of brief advice. There will be variability in the amount of provider contact PC-TAU participants receive, therefore we will closely measure the number and type of PC-TAU contacts and consider it as a covariate in our analyses.

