More structured interventions were considered as comparison conditions to provide tighter control over the interventions and maximize internal validity. However, we opted not to manualize or alter PC-TAU as this would result in comparing two experimental treatments and would not answer our primary research question: Is PC-TIME superior to existing PC-based treatment? The advantages of using the PC-TAU control are that it 1) provides an efficacy evaluation in a real-world practical setting, 2) optimizes the generalizability of findings to other VAs, as the PC-TAU services at our sites are representative of most VA PC settings, 3) controls for non-specific factors such as interaction with the VA staff and receiving treatment that is problem-specific (e.g., Brief Advice for alcohol use), and 4) does not deprive veterans of receiving usual care services.

Statistical Analysis Plan

For this treatment development grant application, assessment of feasibility and acceptability of the intervention and research procedures is the primary goal. As this trial will provide us with feasibility information for a larger trial, we will describe the number of participants screened and enrolled per month, proportion of screened participants who are eligible to enroll, completion rates of follow-up assessments, retention rates in study conditions, and the rate and timing of patient drop-out. Graphs will be utilized to display rates of intervention and assessment retention at each measurement time. Confidence intervals (95%) will be calculated and used in design considerations of a larger trial. Participant retention rates in both study interventions will be described with mean, standard deviations and confidence intervals. PC-TIME therapist fidelity will be described quantitatively with the mean number of items endorsed on fidelity checklists. Items with lower fidelity will be described to inform future PC-TIME training curriculums. For client satisfaction total CSQ scores and scores on individual CSQ items will be described with means, standard deviations and confidence intervals to understand the satisfaction and acceptability in each condition.

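### The plan does not commit to counting VA primary care and PCMHI contacts in the PC-TIME arm, so an add-on effect cannot be told from a replacement effect

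*Combined protocol and SAP*

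**What the plan says.** **Contact measurement (C6.2).** The control-condition section says that there will be "variability in the amount of provider contact PC-TAU participants receive, therefore we will closely measure the number and type of PC-TAU contacts". The same sentence goes on to say that the investigators will "consider it as a covariate in our analyses". C6.1, which describes the PC-TIME arm, has no matching statement. It also does not say whether usual PC or PCMHI care continues there.

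**Administrative extraction (C5.4).** VA data are "extracted to assess if treatment condition relates to engagement in specialty mental health and substance use visits". The next sentence reads: "Number of visits attended and prescriptions of psychiatric and substance use medications between enrollment and 20 week follow-up will be extracted for each participant". It covers both arms, and it does not itself restrict the type of visit.

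**Self-report (C5.4).** "participants will be asked about non-VA treatment at each assessment point using the Treatment Services Review". This does not reach care given inside VA.

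**Access to PCMHI.** C6.2 says that patients positive on either routine screen are offered a PCMHI referral. C4.4 recruits from screen-positive patients. The psychotherapy exclusion in C4.1 applies only to therapy delivered outside primary care.

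**The question.** C6.2 gives the primary research question as: "Is PC-TIME superior to existing PC-based treatment".

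**The concern.** The research question sets PC-TIME against the treatment that primary care already provides. Interpreting the answer requires knowing how much of that treatment each arm received. If PC-TIME participants also use PCMHI, the trial compares PC-TIME plus usual care with usual care. If PC-TIME takes the place of PCMHI contact, the trial compares one with the other. These are different conclusions and would point to different comparators in the full-scale trial that this pilot is meant to inform.

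C6.2 ties contact measurement to PC-TAU participants, and C5.4 names only specialty care as its purpose. A team following the plan literally could reach week 20 with PC-based contact recorded in one arm only.

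The covariate clause adds a second problem. A contact count kept for PC-TAU participants alone has no defined value for PC-TIME participants in a two-arm model. A count kept in both arms arises after randomization and may be affected by assignment. Adjusting for it could remove part of the treatment effect or introduce bias.

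**Working it through.** The plan gives no figure for PC or PCMHI contact in the PC-TIME arm, so there is none to reproduce. The check has two parts: what each source covers, and what one-sided counting leaves undetermined.

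**1. Coverage of VA PC and PCMHI contacts**

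| Source | Participants | Type of care |
|---|---|---|
| C6.2 contact count | PC-TAU, by its stated reason | Provider contact, number and type |
| C5.4 VA extraction | All | Stated aim is specialty care; the wording on visits is not expressly limited |
| C5.4 Treatment Services Review | All | Non-VA treatment only |

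C6.2 treats PCMHI as care within the PC clinic that may come before referral to specialty care, so the stated aim of C5.4 does not include it. No row is an express commitment to count VA PC and PCMHI contacts in the PC-TIME arm.

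**2. Session arithmetic**

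Inputs:
- PC-TIME sessions scheduled: 5 (Statistical Analysis Plan, completer definition).
- PCMHI sessions: 4 on average, for PTSD patients (C6.2).
- q, the share of PC-TIME participants who also use PCMHI: assumed.
- p, the share of PC-TAU participants who use PCMHI: assumed.

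With full attendance, mean PC-based sessions in the PC-TIME arm are 5 + 4q. If PCMHI is not counted there, 4q is missing.

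| q | 5 + 4q | Unrecorded, 4q | 4q / (5 + 4q) |
|---|---|---|---|
| 10% | 5.4 | 0.4 | 7% |
| 30% | 6.2 | 1.2 | 19% |
| 50% | 7.0 | 2.0 | 29% |

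The true difference between arms in total sessions is 5 + 4q − 4p. If only p is observed, q can lie anywhere from 0 to 1, and the difference lies between 5 − 4p and 9 − 4p. At p = 1 that is 1 to 5 sessions. Pure replacement (q = 0) gives 1 and full add-on (q = 1) gives 5, and PC-TAU counts alone cannot separate them.

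**3. What this could mean for an effect estimate**

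Assume that PC-TIME and PCMHI are equally effective at d = 0.5, that effects add, and that all PC-TAU participants receive PCMHI. The head-to-head difference is then 0. The expected difference between arms is (0.5 + 0.5q) − 0.5 = 0.5q: 0 at q = 0, 0.25 at q = 0.5, and 0.5 at q = 1. The same pair of treatments can therefore look equivalent or moderately different, depending on a quantity that the plan does not commit to measuring.

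**The case against.** The strongest reply is that collection in both arms may well be intended. The C5.4 sentence on visits covers each participant and is not expressly limited to specialty care. A covariate in the two-arm growth models of D1 would need values in both arms. The phrase for PC-TAU contacts could mean contacts of the usual-care type in either arm. C4.5 also says that the follow-ups are partly meant to track use of further treatment. These points stand. A reader might infer that PCMHI care in the PC-TIME arm will go uncounted, but the documents do not support that as fact. They show only that no commitment to count it is stated. Section C1.2, which C6.1 cites for the intervention, is not in the available text, so whether PC-TIME participants actually use PCMHI is unknown.

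Three other stronger readings also fail:
- That every participant will have had the same Brief Advice. C6.2 links it to an AUDIT-C score of 4 or more, while C4.4 accepts patients positive on the PC-PTSD alone.
- That one-sided counting always understates the difference between arms. With q = p = 50%, the total-contact difference is 7.0 − 2.0 = 5.0 but would be counted as 5.0 − 2.0 = 3.0, an understatement. The usual-care difference is 2.0 − 2.0 = 0 but would be counted as 2.0 − 0 = 2.0, an overstatement. The direction depends on the summary used.
- That the randomized comparison is invalid. It is not.

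It is also fair to say that feasibility and acceptability are the primary goal and that the pilot's effect sizes are only one input to a later trial. This limits the weight of the point. It does not remove it, because the later trial's comparator depends on which contrast the pilot estimated.

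**Conclusion.** The concern holds as a gap in commitment and interpretation. The plan does not undertake to count VA PC and PCMHI contacts in the PC-TIME arm, and that care is not excluded there in the available text. The intent-to-treat estimate remains valid as the effect of assignment to PC-TIME with usual care available, and no test or sample size changes. What is lost is the ability to say whether an observed benefit reflects addition to, or replacement of, existing PC-based treatment. The covariate use in C6.2 needs changing under either reading of who is counted.

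The size cannot be fixed from the documents. The range of 0.4 to 2.0 unrecorded sessions per PC-TIME participant (7% to 29% of PC-based sessions) rests on an assumed q of 10% to 50%, on full attendance at PC-TIME, and on applying the usual-care average of 4 sessions to people who are also receiving PC-TIME. The effect illustration rests on the further assumptions listed with it. The change is worth making because it is cheap and widens what the trial can conclude.

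**What to change.** 1. In C5.4 and C6.2, state that VA PC and PCMHI contacts (number, type and date) are extracted for every participant in both arms from randomization to week 20, and recorded separately from PC-TIME study sessions.
2. In C6.1, state in advance whether usual PC and PCMHI care remains available to PC-TIME participants. Name the contrast from that statement. Do not choose the wording from the observed counts, since that would settle the trial's question after seeing the data.
3. Tabulate contacts by arm for weeks 0–8 and 8–20 and use them descriptively. Remove contact as a covariate from the primary models.

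Cost: a wider query on administrative data that the trial already plans to extract, some programming to separate study sessions from routine encounters, and one table. The team should confirm that the HIPAA authorization covers the wider query, because its scope is not given. The extraction itself adds no assessment for participants.

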AUDIT score ≥ 15 , 2) PCL-5 ≥ 50 , 3) gender. Demographic and severity cut-points are informed by distributional data from previous study databases. We have used these variables in previous studies with success at obtaining similar groups in each treatment condition at baseline.

Following randomization participants will complete the Clinical Administered PTSD Scale (CAPS-5). While a CAPS-5 is not needed to determine study inclusion, it will serve as the primary PTSD outcome measure because it is a more sensitive measure of PTSD severity than the PCL-5 self-report. We carefully considered whether PTSD diagnosis with the CAPS-5 should be required for study inclusion and decided that using the established cut-point on the PCL-5 provided a more ecologically valid measure for a PC-based study. A 1-hour clinical interview such as the CAPS-5 could not feasibly be used in typical PCMH practice.

A post-treatment assessment (8 weeks) and two follow-up assessments (14 weeks; 20 weeks) will be conducted following baseline (Table 5). For a brief treatment like PC-TIME, we expect the largest treatment effects (for both alcohol use and PTSD) to be at post-treatment. The purpose of follow-ups are to examine if change is maintained and to assess engagement in additional treatment. Our four assessment points will allow for a more precise trajectory of change overtime. We chose 20 weeks for our final follow-up because this is the longest interval that our study timeline would allow. Follow-ups will be in person or by phone (based on participant preference) by study staff and were designed to reduce participant burden and minimize drop-out.

C4.6. Participant Payment. Participants will be paid for time spent completing assessments at a rate of approximately \$20/ hour (baseline session- \$40, post-treatment (week 8)- \$40, 14-week follow-up- \$20, 20-week follow-up- \$20, \$20 bonus for completing all study procedures) and can earn up to \$160. Reimbursement will be by check mailed to the veteran's home. Participants will not be reimbursed for intervention sessions.

C5. Measures

C5.1. Screening Measures

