We do expect to observe a linear or curvilinear decrease in heavy drinking and PTSD severity with a significant treatment effect such that the aggregate trajectory for the PC-TIME condition will demonstrate the greatest reduction (steepest slope) of drinking behaviors and PTSD severity. We also anticipate observing a significant interaction effect where we expect no differences in the mean intercept between the groups at baseline but group differences in the mean slope or trajectory of change over time. In preliminary analyses, we will examine the equivalence of the random assignment of groups with regards to key baseline characteristics. This will involve comparison of treatment groups on sociodemographic characteristics and alcohol-related variables. In the unlikely event that groups differ significantly on any characteristics we will run analyses with indicated covariates to control for baseline differences on outcomes. Attrition effects will be evaluated by testing whether systematic differences exist between participants who complete the research and those who drop out to determine the nature of the potential bias introduced by attrition. Based on prior trials, we anticipate the level of attrition will be low (<15%) and equal across groups (see D3 for missing data). Data analysis will follow a sequence designed to answer the primary outcome question: "Does PC-TIME reduce heavy drinking and PTSD severity relative to PC-TAU?" All analyses assume two-tailed alpha = .05.

We will test the effects of PC-TIME, compared to PC-TAU, on primary variables (percentage of heavy drinking days, average number of drinks per drinking day, a dichotomous variable indicating whether one's past 30-day drinking pattern would be classified as excessive (see C5.2), PTSD severity, and drinking-related problems at post-treatment. Depending on the nature of the variable, the analyses will use either a normal distribution (e.g., for the SIP and PCL-5) or a Poisson or negative binomial model for count data (e.g., number of drinks). The intervention condition will be dummy-coded using PC-TAU as the reference group and will be included as a time-invariant covariate on Level 2 of the multilevel growth model ⁹⁴. If any covariates are identified as necessary during preliminary analyses, these will also be included in the model.

D3. Missing Data

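### Adjusting the arm comparison for PC-TAU contacts, which arise mainly after randomization and are part of the comparator, can shift the post-treatment estimate in either direction

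*Combined protocol and SAP*

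**What the plan says.** Section C6.2 defines PC-TAU as annual screening, Brief Advice after a positive AUDIT-C, and an offered referral to the PCMHI provider, with 4 PCMHI sessions on average for PTSD patients. It then notes: "There will be variability in the amount of provider contact PC-TAU participants receive", and for that reason "we will closely measure the number and type of PC-TAU contacts and consider it as a covariate in our analyses". No time window, coding for PC-TIME participants, or limit to secondary or exploratory analyses is given.

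The same section explains the choice of comparator: "we opted not to manualize or alter PC-TAU", because the question is "Is PC-TIME superior to existing PC-based treatment".

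The SAP makes the primary analyses intent-to-treat. Section D1 fits a growth model with time, treatment and their interaction, and says "we expect no differences in the mean intercept between the groups at baseline". It adds a test at post-treatment: "We will test the effects of PC-TIME, compared to PC-TAU, on primary variables". Its explicit covariate step concerns baseline imbalance, but a later sentence is open: "If any covariates are identified as necessary during preliminary analyses, these will also be included in the model". PC-TAU contacts are neither named nor excluded.

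**The concern.** Usual-care contacts are what the control arm receives. Holding them constant replaces the stated question with a different one: how the arms would compare at equal contact. The variation removed is the variation that C6.2 chose to keep.

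The contacts also arise mainly after assignment, so they can depend on arm and on how ill the patient is. A covariate of that kind does not enjoy the protection of randomization.

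The post-treatment contrast is the most exposed. Section C4.5 states "we expect the largest treatment effects (for both alcohol use and PTSD) to be at post-treatment", D1 tests the primary variables there, and under C5.2 it is the only follow-up for CAPS-5, the primary PTSD measure. The SAP also plans to use between-arm effect sizes at each assessment to help size the next trial, so a contact-adjusted estimate used there would carry its bias forward.

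**Working it through.** **Plan's own figures.** The documents give no expected arm difference in contacts, no correlation with outcome and no effect size. The one sample-size figure reproduces (60 × 0.85 = 51) but is not at issue. All sizes below rest on assumptions and are illustrative.

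**Timing.** The covariate is motivated by contact that participants assigned to PC-TAU will receive, and C5.4 extracts visits from enrollment to week 20. Screening, and probably Brief Advice, precede enrollment for patients recruited from positive screens. Hence mainly, not wholly, post-randomization.

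**Model 1: D1 growth model; contacts do not affect outcome but track the patient's own course.**

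Assumed: 30 per arm; outcome in SD units, higher is worse; random-intercept variance 0.5, slope SD 0.6 over 20 weeks, residual variance 0.5; weeks 0, 8, 14, 20. The true effect is -0.50 at week 20, hence -0.50 × 8/20 = -0.20 at week 8. Contact SD is 2, and PC-TAU has D = 2 more contacts. The correlation r is with (a) the patient's own slope or (b) the patient's own baseline level.

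A main-effect contact term with coefficient γ gives: adjusted contrast = unadjusted contrast + γ × D.

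- Case (b): γ = r × √0.5 / 2 = 0.3 × 0.707 / 2 = 0.106. Shift = 0.106 × 2 = 0.21.
- Case (a): γ = r × 0.6 / 2 × t̄, where t̄ is the GLS-weighted mean time, 1′V⁻¹t / 1′V⁻¹1. With t = (0, 0.4, 0.7, 1) and V = 0.5·11′ + 0.36·tt′ + 0.5·I, this is 0.541 / 1.436 = 0.377. Shift = 0.3 × 0.6 / 2 × 0.377 × 2 = 0.068.

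Simulated large-sample fits gave 0.214 and 0.067.

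| r | Week-8 contrast, (a) | Week-8 contrast, (b) |
|---|---|---|
| no contact term | -0.20 | -0.20 |
| +0.3 | -0.13 | +0.01 |
| +0.1 | -0.18 | -0.13 |
| -0.3 | -0.27 | -0.41 |

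A 1-contact difference halves the shifts, no difference removes them, and more contacts in PC-TIME reverses their sign. Coding PC-TIME as zero with a PC-TAU mean of 2 gives the same shifts. The baseline contrast, truly 0, becomes +0.07 (a) or +0.21 (b) at r = +0.3, where D1 expects none.

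**Slope.** A time-invariant main-effect term leaves it at -0.50. Only a contacts-by-time term would move it: in case (a), by 0.3 × 0.6 / 2 × 2 = 0.18, to -0.32 (or -0.68 at r = -0.3). The documents do not propose that term.

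**Error rate.** The week-8 SE is about 0.21 unadjusted and 0.24 adjusted. With no true effect, the shift in SE units is 0.068 / 0.241 = 0.28 (a) or 0.212 / 0.241 = 0.88 (b). The normal approximation then gives two-sided rejection of about 6% and 14%. Simulation of 4,000 trials gave 5.8% and 13.4%, against 4.6% and 5.1% unadjusted.

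**CAPS-5, two time points, true effect -0.50 at week 8, slope SD 0.6 taken over those 8 weeks.** The post-treatment contrast becomes -0.43 (a) or -0.29 (b). The estimate of change is unaffected.

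**Model 2: single post-treatment comparison, 60 patients, PC-TAU mean 4 contacts, direct PC-TIME effect -0.50, PC-TIME contacts coded 0.**

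- Contacts help by 0.1 SD each: the true total effect against usual care is -0.50 + 0.1 × 4 = -0.10; the adjusted estimate is -0.50.
- Contacts inert, sicker patients get more: -0.50 becomes -0.02.
- Contacts inert, sicker patients get fewer: -0.50 becomes -0.97.
- Contacts help and sicker patients get more: -0.10 becomes -0.02, as the biases partly cancel.

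With equal mean contacts in both arms (4 and 4) the shift is zero in every scenario.

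**The case against.** The strongest reply is that this is one optional sentence in a treatment description. The D1 covariate rule reads most naturally as concerning baseline imbalance, the SAP's effect sizes at each assessment are described without covariates, and the primary analyses are intent-to-treat. The expected interaction is barely touched by a main-effect contact term, and neither is CAPS-5 change. The larger shifts need a full 1-SD arm difference in contacts and a correlation of 0.3; at r = 0.1 they are 0.02 to 0.07 against an SE of 0.21. The assumed effect grows to week 20, whereas C4.5 expects it to peak at post-treatment. Only normal outcomes were examined, while D1 also plans count models and a dichotomous outcome.

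Much of this stands and limits the weight of the point. The slope result should not be extended to the count and binary models without checking. The time course of the true effect does not matter, because the shift does not depend on it. None of the cited text bars the adjustment: intent-to-treat settles who is analysed, not which covariates enter, and D1 admits any covariate found necessary. The level contrast at post-treatment, which D1 tests explicitly, remains exposed.

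**Conclusion.** The concern holds. The plan leaves open adjusting the treatment comparison for a component of the comparator that is observed mainly after randomization. If contacts differ by arm or are counted only in PC-TAU, the post-treatment contrast can move in either direction. With a 2-contact difference and a correlation of 0.3 in size, the move is about one third of a standard error to nearly one standard error. With equal contacts counted alike there is no bias. The sizes depend on assumed inputs; the reading of the text does not. The point should be corrected, but it does not threaten the trial's main deliverable, which is feasibility.

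**What to change.** 1. In C6.2, replace the covariate clause with: *in both arms and report them descriptively by arm; any analysis relating contacts to outcome will be labelled exploratory and kept outside the treatment-comparison models*.
2. In D1, state that covariates in the treatment-comparison models are limited to pre-randomization variables, for example the urn factors (AUDIT ≥ 15, PCL-5 ≥ 50, gender). Baseline CAPS-5 is done after randomization but stays in the growth model as the time-0 outcome, so this limit does not remove it.
3. Minor: the completer rule of 4 of 5 sessions comes from the PC-TIME manual and has no PC-TAU counterpart. Report completers descriptively within PC-TIME, not as a between-arm contrast.

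The cost is small: no added participants or visits. Little precision is lost; with no arm difference and r = 0.3 in case (b), the week-8 SE is 0.218 unadjusted against 0.213 adjusted. The sponsor must confirm that record extraction captures primary-care contacts (Brief Advice, PCMHI) in both arms. C5.4 names specialty visits and prescriptions, so a small addition for up to 60 participants over 20 weeks may be needed.
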